5.1.2 Additional study treatment

No additional treatment beyond investigational treatment is requested for this trial.

5.2 Treatment arms

- Period 1:

VAL489 (Valsartan) 0.25 mg/kg or 4 mg/kg

VAL489 (Valsartan) 0.25 mg/kg or 4 mg/kg matching placebo

- Period 2:

VAL489 (Valsartan) 1 mg/kg, optional titration 2 mg/kg, 3 mg/kg and 4 mg/kg (max dose).

5.3 Treatment assignment, randomization

At Visit 2, all eligible patients will be randomized via Interactive Voice Response System to one of the treatment arms. The investigator or his/her delegate will contact the IRT after confirming that the patient fulfills all the inclusion/exclusion criteria. The IRT will assign a randomization number to the patient, which will be used to link the patient to a treatment arm and will specify a unique medication number for the first package of study drug to be dispensed to the patient. The randomization number will not be communicated to the caller.

The randomization numbers will be generated using the following procedure to ensure that treatment assignment is unbiased and concealed from patients and investigator staff. A patient randomization list will be produced by the IRT provider using a validated system that automates the random assignment of patient numbers to randomization numbers. These randomization numbers are linked to the different treatment arms, which in turn are linked to medication numbers. A separate medication list will be produced by or under the responsibility of Novartis Drug Supply Management using a validated system that automates

the random assignment of medication numbers to study drug packs containing each of the study drugs.

The randomization scheme for patients will be reviewed and approved by a member of the IIS Randomization Group.

5.4 Treatment blinding

Patients, investigator staff, persons performing the assessments, and data analysts will remain blind to the identity of the treatments from the time of randomization up to Visit 5 (Week 6) using the following methods.

1. Randomization data are kept strictly confidential until the time of unblinding, and will not be accessible by anyone else involved in the study.
2. The identity of the treatments will be concealed by the use of study drugs that are all identical in packaging, labeling, and schedule of administration and appearance.

A double-dummy design is used because the identity of the study drugs cannot be disguised due to their different forms.

Unblinding will only occur in the case of patient emergencies (see [Section 5.5.10](#)) and at the conclusion of the study.

An assessment will be done by the appropriate site personnel and the CTH for any patient whose treatment code has been broken inadvertently or for any non-emergency reason to assess whether or not study drug should be discontinued and, if applicable, whether the patient can continue into the next trial phase (e.g., open-label extension).

Starting from Visit 5 (Week 6) up to Visit 11 (Week 26) the identity of the treatments will be open-label.

5.5 Treating the patient

5.5.1 Patient numbering

Each patient is uniquely identified by a Subject Number which is composed by the site number assigned by Novartis and a sequential number assigned by the investigator. Once assigned to a patient, the Subject Number will not be reused.

Upon signing the informed consent form, the patient (parent) is assigned the next sequential number by the investigator. The investigator or his/her staff will contact the IRT and provide the requested identifying information for the patient to register them into the IRT.

If the patient fails to be treated for any reason, the IRT must be notified within 2 days that the patient was not treated. The reason for not being treated will be entered on the Screening Log CRF.

5.5.2 Dispensing the investigational treatment

Each study site will be supplied by Novartis with study drug in packaging of identical appearance.

The investigational treatment packaging has a 2-part label. A unique randomization number is printed on each part of this label which corresponds to one of the “n” treatment arms and a specific visit. Investigator staff will identify the investigational treatment package(s) to dispense to the patient by contacting the IRT and obtaining the medication number(s). Immediately before dispensing the package to the patient, investigator staff will detach the outer part of the label from the packaging and affix it to the source document (Drug Label Form) for that patient’s unique subject number.

5.5.3 Handling of study treatment

5.5.3.1 Handling of investigational treatment

Investigational treatment must be received by a designated person at the study site, handled and stored safely and properly, and kept in a secured location to which only the investigator and designees have access. Upon receipt, all investigational treatment should be stored according to the instructions specified on the labels. Clinical supplies are to be dispensed only in accordance with the protocol.

Medication labels will be in the local language and comply with the legal requirements of each country. They will include storage conditions for the investigational treatment but no information about the patient except for the medication number.

The investigator must maintain an accurate record of the shipment and dispensing of investigational treatment in a drug accountability log. Monitoring of drug accountability will be performed by the field monitor during site visits and at the completion of the trial. Patients will be asked to return all unused investigational treatment and packaging at the end of the study or at the time of discontinuation of investigational treatment.

At the conclusion of the study, and as appropriate during the course of the study, the investigator will return all unused investigational treatment, packaging, drug labels, and a copy of the completed drug accountability log to the CRO monitor or to the Novartis address provided in the investigator folder at each site.

5.5.4 Instructions for prescribing and taking study treatment

The investigator should insure that the patient’s parent or guardian clearly understands the following dosing instructions:

Study drug will be dispensed at Visits 2, 3, 4, 5, 7, 8, 9 and 10. All study medication will be supplied in the form of an oral solution.

This study consists of two periods:

- Period 1: valsartan 0.25 mg/kg or 4 mg/kg and valsartan matching placebo 0.25 mg/kg or 4 mg/kg
- Period 2: valsartan 1 mg/kg open label, optional 2 mg/kg, 3 mg/kg and 4 mg/kg (max. dose).

Starting at Visit 7 (Week 10) valsartan will be optionally titrated from 1 mg/kg to 2 mg/kg. Valsartan will continue to be optionally up titrated in 1 mg/kg increments every 4 weeks (visits 8, 9 and 10) until maximum dose of 4 mg/kg is achieved. Titration criteria can be found in section 3.1.

Additionally, all dosages prescribed and dispensed to the patient and all dose changes during the study must be recorded on the Dosage Administration Record CRF.

All kits of investigational treatment assigned by the IRT will be recorded/databased in the IRT.

The investigator should promote compliance by instructing the patient to take the study drug exactly as prescribed and by stating that compliance is necessary for the patient's safety and the validity of the study. The patient should be instructed to contact the investigator if he/she is unable for any reason to take the study drug as prescribed.

First dose of study medication should be administered at Visit 2, after all study visit assessments have been completed. All study treatment will be taken orally and will be administered once daily, at approximately the same time each day, in the morning, with or without food, except on the days of study visits. On the days of study visits the study drug should be taken after all study visit assessments have been completed (see [Section 6](#)).

5.5.5 Permitted dose adjustments and interruptions of study treatment

The open-label study medication doses ([Figure 3-1](#)) may be down titrated, at the investigator's discretion. After down titration the investigator may up titrate again but cannot exceed the maximum dose of 4 mg/kg of valsartan.

Study drug treatment interruptions are only allowed for safety reasons.

All changes in study drug must be recorded on the Dosage Administration Record CRF.

5.5.6 Rescue medication

No rescue medication will be allowed.

Background antihypertensive medication other than RAAS blockers are allowed from screening through the end of study.

Use of background antihypertensive medication must be recorded on the Prior and concomitant anti-hypertensive medications CRF.

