	
hypertension, with or without CKD.
 
• To assess the effect of valsartan on proteinuria and eGFR in a subset of children with hypertension and CKD
Secondary Objectives	Refer to above
Study design	
This is a 6 week, randomized, multicenter, double-blind, double-dummy study to evaluate the dose response of valsartan solution on blood pressure reduction in children 1-5 years old with hypertension, with or without chronic kidney disease, followed by a 20 week open-label phase with an optional titration period.
 
Period 1 is a 6 week double-blind dose- ranging period to ensure that the maximum antihypertensive effect of valsartan will be reached. Period 2 is an open-label optional titration phase, where the safety of valsartan can be assessed including potential effects on proteinuria.
 
Patients entering the study receiving background antihypertensive treatments may continue on these medications as long as they meet the eligibility criteria for MSBP ($\geq 95^{\text{th}}$ percentile). The background therapy and dose should remain unchanged for the duration of the study. No patients will be permitted in the study with background RAAS blocker therapy (ARBs, ACEi, DRLs).
 
This study consists of three periods:
 
A Screening period of up to 28 days
 
Period 1: A six-week randomized, double-blind, double-dummy dose-ranging period consisting of 2 valsartan dose groups (0.25 mg/kg and 4 mg/kg), and randomization will be 1:1.
 
Period 2: A 20 week open-label titration phase where all patients will start with 1 mg/kg valsartan for four weeks then be optionally titrated every four weeks. Patients may receive up to 4 mg/kg of valsartan.

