3.1 Study design

This is a 6 week, randomized, multicenter, double-blind, double-dummy study to evaluate the dose response of valsartan solution on blood pressure reduction in children 1-5 years old with hypertension, with or without chronic kidney disease, followed by a 20 week open-label phase with an optional titration period. [Figure 3-1](#) shows the overall study design.

[figure not shown]
Period 1 is a 6 week double-blind dose ranging period to ensure that the maximum antihypertensive effect of valsartan will be reached. Period 2 is an open-label optional titration phase, where the safety of valsartan can be assessed including potential effects on proteinuria.

Patients entering the study receiving background antihypertensive treatments may continue on these medications as long as they meet the eligibility criteria for MSBP ($\geq 95^{\text{th}}$ percentile). The background therapy and dose should remain unchanged for the duration of the study. No patients will be permitted in the study with background RAAS blocker therapy (ARBs, ACEi, DRIIs).

This study consists of three periods:

- A Screening period of up to 28 days
- Period 1: A six-week randomized, double-blind, double-dummy dose-ranging period consisting of 2 valsartan dose groups (0.25 mg/kg and 4 mg/kg), and randomization will be 1:1.
- Period 2: A 20 week open-label titration phase where all patients will start with 1 mg/kg valsartan for four weeks then be optionally titrated every four weeks. Patients may receive up to 4 mg/kg of valsartan.

Figure 3-1 Study design

Screening

A screening visit (Visit 1) will be performed 1 to 28 days before enrollment to test eligibility for study participation. A parent/guardian of the patient will sign the Informed Consent Form after the purpose and nature of the study has been clearly explained to them.

Washout period

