Under the supervision of the study investigator, a wash-out period of 28 days will be included for eligible patients on prior treatments that inhibit the renin angiotensin aldosterone system (RAAS blockers), which include angiotensin receptor blockers (ARB), angiotensin converting enzyme inhibitors (ACEi) and direct renin inhibitors (DRI). During the wash-out period patients should come to the clinic approximately once a week for safety blood pressure measurements. If MSBP rises more than 20% above the 95th percentile for age, gender and height during wash-out, or if the investigator deems hypertensive treatment necessary, then the patient may commence with the study drug treatment earlier, once all eligibility criteria have been met.

Patients currently taking antihypertensive medications other than RAAS blockers, who have a MSBP <95th percentile for age, gender and height at screening, can be tapered off these medications according to investigator instruction and manufacturer's labeling, in order to meet entry criteria. Patients who are **not** on RAAS inhibitor therapy can enter the treatment phase of the trial (Visit 2) once the patient has achieved a MSBP ≥ 95th percentile for age, gender and height, screening laboratory results have been received and reviewed, and all other inclusion criteria have been met. Patients currently taking non-RAAS blockers, who have a MSBP ≥ 95th percentile for age, gender and height, can continue taking these antihypertensive medications throughout the trial provided their dose remains unchanged.

Dose ranging period (Period 1):

Patients should be seen in the clinic on a weekly basis during screening, to determine if they meet the blood pressure criteria (MSBP \geq 95th percentile) for randomization. Qualified patients will be randomized and all Visit 2 procedures completed. If the patient's blood pressure does not meet criteria, the patient can return to the research center once a week for a qualifying blood pressure evaluation for up to 28 days, beyond which they will be considered a screen failure.

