4.1 Inclusion criteria

Patients eligible for inclusion in this study have to fulfill all of the following criteria:

1. Written informed consent must be obtained before any assessment is performed.
Parent(s)/guardian(s) have to provide consent in writing (written informed consent) after the purpose and nature of the study has been clearly explained to them.
2. Male or female, 1 to 5 years at baseline (visit 2), with a documented diagnosis of hypertension ([National High Blood Pressure Education Program 2004](#))
3. CKD patients must be defined as any of the following criteria ([Hogg et al 2003](#)) (At least 50% of enrolled patients will be CKD-patients):
 - a. Kidney damage for ≥ 3 months, as defined by structural or functional abnormalities of the kidney, with or without decreased GFR, manifested by one or more of the following features:
 - Abnormalities in the composition of urine
 - Abnormalities in imaging tests
 - Abnormalities on kidney biopsy
 - b. Estimated GFR < 60 mL/min/1.73m² (calculated by Modified Schwartz Formula) for ≥ 3 months, with or without the other signs of kidney damage described above.
4. MSBP (mean of 3 measurements) must be $\geq 95^{\text{th}}$ percentile, and $\leq 25\%$ above the 95^{th} percentile, for age, gender and height, at baseline (visit 2) ([Appendix 2](#)), by office automatic blood pressure monitor and cuff, provided by the Sponsor. Confirmation of MSBP $\geq 95^{\text{th}}$ percentile must be made using the auscultatory blood pressure method.
5. Able to swallow the valsartan solution
6. Body weight must be ≥ 8 kg and ≤ 40 kg at baseline
7. Must be able to safely washout prior ARB, ACEi and DRI therapy (if applicable) and other antihypertensive therapy (if applicable)

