4.2 Exclusion criteria

Patients fulfilling **any** of the following criteria are not eligible for inclusion in this study. No additional exclusions may be applied by the investigator, in order to ensure that the study population will be representative of all eligible patients.

1. Any clinically significant physical abnormality or clinically relevant abnormal laboratory values (other than those relating to renal function) obtained at the screening visit (Visit 1), including the following:
 - a. AST/SGOT or ALT/SGPT > 3 times the upper limit of the reference range. Patients known to have active or chronic hepatitis will be excluded.
 - b. Total bilirubin > 2 times the upper limit of the reference range
 - c. Estimated Glomerular Filtration Rate [eGFR] < 30 mL/min/1.73m² (calculated using Modified Schwartz Formula)

- d. WBC count <3000/mm³
- e. Platelet count <100,000/mm³
- f. Serum potassium >5.3 mmol/L
- g. Hemoglobin <9 g/dL

2. Uncontrolled diabetes mellitus, as defined by the investigator
3. Unilateral, bilateral and graft renal artery stenosis
4. Current diagnosis of heart failure (NYHA Class II-IV)
5. Patients taking any of the following concomitant medications following screening:
 - a. RAAS blockers other than study drug
 - b. Lithium
 - c. Potassium-sparing diuretics, potassium supplements, salt substitutes containing potassium and other substances that may increase potassium levels
 - d. Non-steroidal anti-inflammatory drugs (NSAIDS), including selective COX-2 inhibitors, acetylsalicylic acid >3g/day, and non-selective NSAIDs (paracetamol/acetaminophen is permitted)
 - e. Antidepressant drugs in the class of MAO inhibitors (e.g. phenelzine)
 - f. Chronic use of stimulant therapy for ADD/ADHD
6. Patients who demonstrate clinically significant ECG abnormalities such as concurrent potentially life threatening arrhythmias or symptomatic arrhythmias are excluded, as are patients with second or third degree heart block without a pacemaker. Patients with ECG abnormalities associated with left ventricular hypertrophy are permitted to enroll.
7. Patients who have coarctation of the aorta with a gradient of ≥ 30 mmHg

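### Protocol 3.1 and 5.5.6 permit potassium-sparing diuretics that exclusion 5c and Table 5-1 bar, and 5.5.8 lets RAAS blockers be stopped at Visit 2 despite the 28-day washout in 3.1

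*Protocol*

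**What the plan says.** **Permission.** The synopsis and Section 3.1 state: "Patients entering the study receiving background antihypertensive treatments may continue on these medications", subject to the systolic pressure criterion and an unchanged dose. The only drug-class exception is "No patients will be permitted in the study with background RAAS blocker therapy". The washout text in 3.1 repeats the permission: children on non-RAAS drugs who meet the pressure criterion "can continue taking these antihypertensive medications throughout the trial provided their dose remains unchanged". Section 5.5.6 restates it without conditions: "Background antihypertensive medication other than RAAS blockers are allowed from screening through the end of study".

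**Prohibition.** Exclusion criterion 5c (Section 4.2) excludes children who, following screening, take "Potassium-sparing diuretics, potassium supplements, salt substitutes containing potassium and other substances that may increase potassium levels". Table 5-1 in Section 5.5.8 repeats that item in a row of its own, separate from RAAS blockers, and the ban runs to the end of the study.

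**Timing.** Section 3.1 provides that "a wash-out period of 28 days will be included for eligible patients on prior treatments that inhibit the renin angiotensin aldosterone system". It has one relaxation: if systolic pressure rises more than 20% above the 95th percentile, or the investigator judges treatment necessary, "the patient may commence with the study drug treatment earlier, once all eligibility criteria have been met". Section 5.5.8 has a different rule for everything in Table 5-1. Children on a listed drug should not be enrolled, or, where ethically justified, the drug may be stopped before Visit 2 or on that day. The first row of Table 5-1 is RAAS blockers, including aldosterone antagonists.

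**The concern.** Two pairs of rules give different answers to the same question.

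The first is whether a child may stay on a potassium-sparing diuretic. A clinician settling background therapy would naturally look at 3.1 or 5.5.6, and both say yes. Exclusion 5c and Table 5-1 say no. What is at stake is potassium. Section 3.6 already expects some hyperkalemia, because RAAS-active drugs carry that risk and at least half the children will have chronic kidney disease.

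The second is how long a child must be off a RAAS blocker before baseline. Visit 2 is the day of baseline measurement, randomization and first dose. A RAAS blocker stopped that day would still be acting when the baseline value for the primary variable is taken and when valsartan is first given.

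**Working it through.** The plan has no figure to reproduce here. The check compares the texts and adds two day counts.

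**1. Potassium-sparing diuretics**

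- Period: 5.5.6 permits from screening to the end of the study; exclusion 5c and Table 5-1 prohibit after screening, and Table 5-1 carries this to the end of the study. The periods overlap throughout treatment.
- Does the RAAS exception in 3.1 and 5.5.6 already remove these drugs? Table 5-1 lists them apart from RAAS blockers, so on the protocol's own classification it does not.
- Scope: aldosterone antagonists fall outside this conflict. Table 5-1 counts them as RAAS blockers, and the 3.1 washout is defined by mechanism. The direct conflict concerns other potassium-sparing diuretics.
- Cross-reference: none of the permissive sentences points to Section 5.5.8 or Table 5-1, and no text says which rule prevails. The 3.1 sentence admitting children not on RAAS inhibitors to Visit 2 asks for the pressure criterion, reviewed screening laboratory results and the other inclusion criteria. It does not mention the exclusions.

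Result: the same drug is allowed by one rule and barred by another over the same period.

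**2. Time off a RAAS blocker before baseline**

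| Rule | Days off drug at Visit 2 |
|---|---|
| 3.1, standard washout | 28 |
| 3.1, early start (conditional) | fewer than 28 |
| 5.5.8, stopped at Visit 2 | 0 |

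The early start depends on a pressure trigger or the investigator's judgement that treatment is needed. It does not authorise routine withdrawal at Visit 2, so it does not reconcile the first and third rows.

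**3. When the next scheduled potassium falls**

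Section 6.5.4.2 schedules chemistry at Visits 1, 2 and 5 for this part of the trial. Table 6-1 puts Visit 2 at Day 1 and Visit 5 at Day 42. The gap is 42 − 1 = 41 days, before visit windows, with no scheduled potassium. A child wrongly left on a potassium-sparing diuretic could take up to 4 mg/kg for that time, unless an unscheduled test is done.

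**4. Effect on the primary comparison**

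Background therapy is settled before blinded assignment, so either ambiguity reaches both arms alike in expectation. The primary ANCOVA also adjusts for baseline systolic pressure. Neither conflict biases the comparison of 4 mg/kg with 0.25 mg/kg.

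**The case against.** The strongest reply is that the substance is already handled. Exclusion 5c is specific and mandatory, and an excluded child never enters the study to benefit from the general permission. Section 5.3 requires all eligibility criteria to be confirmed before the IRT call, and Section 8.1 requires full verification of eligibility. Background antihypertensives are recorded on a CRF, so a barred drug would be visible. Potassium above 5.3 mmol/L excludes at entry and triggers a repeat test during the trial; a repeat confirming a value above 5.5 mmol/L requires discontinuation. All of this stands, and it is why the risk is residual. It does not remove the conflict, since those checks still rely on staff choosing the right one of two rules.

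On timing, 5.5.8 is generic to every listed drug and is qualified by ethical justification, while 3.1 is the specific RAAS rule and most likely governs. That also stands. But 5.5.8 includes RAAS blockers by name and gives no pointer back to 3.1.

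Two further criticisms might be inferred, and the documents do not support them:

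- *Section 5.5.8 contradicts itself* by banning drugs after screening and then allowing withdrawal up to Visit 2. The protocol describes screening as a period of up to 28 days before enrollment, so the ban can be read as starting when that period ends.
- *Inclusion criterion 7 omits aldosterone antagonists.* It reads "Must be able to safely washout prior ARB, ACEi and DRI therapy (if applicable) and other antihypertensive therapy (if applicable", so it extends beyond the three named classes and needs no edit.

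**Conclusion.** Both conflicts are real, and both are minor. Following 5.5.6 or 5.5.8 literally gives a worse outcome than following exclusion 5c or the 3.1 washout: valsartan given with a potassium-sparing diuretic in the first case, and a baseline taken and valsartan started with a RAAS blocker still acting in the second. The specific rules most likely prevail in practice.

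The documents do not say how many screened children take these drugs, so the number affected cannot be estimated. The only sizes they support are 28 days against 0 days off a RAAS blocker, and 41 scheduled days without a potassium measurement after Visit 2.

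A reader might infer that the treatment comparison is biased or that the trial's power is at risk. The documents do not support either. Allocation is blinded and follows the background-therapy decision, and they contain no data from which a loss of power could be derived. The gain from correction is mainly patient safety, with a cleaner baseline for any child whose RAAS blocker would otherwise be stopped at Visit 2.

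**What to change.** 1. In the synopsis, both places in Section 3.1, and Section 5.5.6, add *except treatments listed in Table 5-1* to the sentences that let background antihypertensives continue.
2. In Section 5.5.8, state that RAAS blockers, including aldosterone antagonists, follow the Section 3.1 washout with its early-start provision.
3. In the same section, state that other Table 5-1 drugs affecting blood pressure or potassium are stopped before Visit 2, not on the day.

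The cost is a few words and a note to sites, with no extra visits, procedures or patients. The small downside is that a few children may enter slightly later within the 28-day screening window. The SAP needs no change: it already summarises prior and concomitant antihypertensives by treatment.
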